## 4.2 Conclusion

In general, results of our pilot study indicate that tDCS is a promising technique to enhance rehabilitative outcomes of the paretic upper limbs in patients with incomplete cervical SCI [60, 61, 65]. Effects of tDCS are related to mechanisms of restoration of balance in excitability—re-emergence of the brain representation of weak muscles and reduction of the brain representation devoted to spared, strong muscles within residual neural resources. What speaks to the scientific rigor of our findings is the evidence that effects of tDCS observed here cannot be explained based on spontaneous shifts in function or excitability, or test-retest effects. Metrics of strength and dexterity and those indexing neurophysiology remained stable in the absence of any intervention. Values of UEMS and TMS metrics showed excellent and moderate-to-excellent reliability during the baseline control phase (concordance correlation coefficient [CCC] = 0.964, and CCC = 0.644 to 0.935, respectively) [60]. Therefore, greater confidence can be placed upon the findings demonstrating promise of tDCS during the intervention phase. Here, our objective is to investigate whether the promise of tDCS, and the mechanisms underlying its effect, observed in our recently published single-center pilot study can be replicated by performing the study at other multiple centers [60, 61, 65]. A multi-center investigation is a natural, logical progression to establish the generalizability of the effect of tDCS across different types of patients and confirm the validity of our findings.

## 5. STUDY DESIGN

Title: Improving Spinal Cord Injury Rehabilitation Interventions by Retraining the Brain

PI: [name]

Sub-site PI's: [name], [name], [name], [name], [name]

Protocol V 5.1 —2/3/2023

## 5.1 Study Objective

The objective of the proposed trial is to extend the scope of our pilot study and conduct a phase I/II multi-site randomized controlled, double-blinded clinical trial to test the safety, feasibility, efficacy, and mechanisms of delivering tDCS with rehabilitation in SCI. At least forty-nine (up to 54) patients with chronic, incomplete (having sparing to muscles in the upper extremities below the level of injury) C1-C8 SCI will be enrolled across 4 sites: Cleveland Clinic (at least 21[up to 25] subjects), Kessler Foundation/Kessler Institute for Rehabilitation (14 subjects), Cleveland VA Medical Center (6 patients), and MetroHealth Hospital (8 patients). Patients will first complete a baseline control phase lasting 3 weeks, during which they will continue with their typical routine and activities (fig. 4). After the baseline control phase, they will be randomly assigned to either receive tDCS ( $n = 22$ ) or sham tDCS ( $n = 22$ ) during rehabilitation. Rehabilitation will be given for 2 hours/day, 5 days/week for 3 weeks. Rehabilitation will especially involve exercises for weak muscles innervated below the level of injury, such as triceps (C7). After the completion of the rehabilitation/intervention phase, patients will participate in a 3-month follow-up phase, during which they will be asked to continue with exercises prescribed as part of the home-exercise routine. Up to 42 age matched healthy control participants will also be enrolled to record ‘normal’ neural indices (15 at the Cleveland Clinic, 6 at Kessler Foundation, 6 at Cleveland VA, and up to 15 at MetroHealth Hospital).

[figure not shown]
Assessments will be completed before and after the baseline control phase (pretests 1/2), the intervention phase (posttest) and the 3-month follow-up phase (follow-up) (fig. 4). Assessments will include metrics of strength and dexterity (Graded Redefined Assessment of Strength, Sensation and Prehension [GRASSP]); functional abilities (Wolf Motor Function Test [WMFT]); activity limitations (self-care subscale of the Spinal Cord Independence Measure [SCIM]); and participation restrictions (Canadian Occupational Performance Measure [COPM]). TMS will be used to study excitability of neural resources devoted to a weaker muscle and a spared muscle. The Hoffmann reflex (H-reflex) involving peripheral electrical stimulation will be used to study spinal excitability. Up to 42 age-matched ( $\pm 5$  years), healthy control subjects will also undergo testing of TMS/H-reflex at a cross-sectional time-point. The goal will be to establish age-based norms for neurophysiologic metrics related to non-dominant biceps and triceps muscles. In accordance with feedback provided by DoD reviewers, adverse effects, SCI-specific symptoms (e.g., pain, autonomic dysreflexia) and attrition and integrity of blinding will also be recorded. The following aims and hypotheses will be tested in the proposed study.

Title: Improving Spinal Cord Injury Rehabilitation Interventions by Retraining the Brain

PI: [name]

Sub-site PI's: [name], [name], [name], [name], [name]

Protocol V 5.1 —2/3/2023

**Fig. 4: Study Design and follow-up procedures.** TMS= Transcranial Magnetic Stimulation; H-reflex= Hoffman Reflex; tDCS= transcranial direct current stimulation (tDCS)

## 5.2 Sample Size Estimation and Power Analysis

Sample size was calculated based on PI [name] recent DoD-funded pilot study [60, 61]. Differences in effect size between tDCS+-rehab and sham+-rehab groups were used to

**Table 2: Sample Size Estimation based on Power Analysis**

	Outcomes/Metrics	Effect size (tDCS vs. Sham)	$\alpha$	80%	85%	90%	95%
Aim 1	UEMS (# Weak muscles showing clinically detectable improvement)	0.938	0.05	40	44	52	62
	$\Delta\%$ Nine Hole Peg Test	1.033	0.05	32	36	42	52
Aim 2	$\Delta\%$ Map Ratio (Weak map/Strong map)	1.192	0.05	26	30	34	40

estimate sample sizes, based on two sample t statistics compiled at  $\alpha = 0.05$  for 80% power (Table 2). For Aim 1, data concerning strength/power of muscles and dexterity (NHPT) was used since both of these metrics are components of the primary outcome for Aim 1 (GRASSP). Based on between-group comparison of the numbers of weak (C6-T1) muscles that achieved clinically detectable improvements on MRC ( $\geq 1$  full grade gain [63, 64]), we would require a total of 40 patients, and based on between-group comparison of % improvement on the NHPT (pegs per second), we would require 32 patients for achieving 80% power. This estimate would be sufficient for Aim 2 as well. For Aim 2, data concerning motor cortical map excitability was used, as this is the primary outcome for Aim 2. Based on between-group comparison of % change in map ratio (weak map/strong map), we would require 26 patients for achieving 80% power. Considering that there could be attrition of 10%, we expect to enroll 44 patients. A sample of 44 patients with 22 patients included in each SCI group would also be sufficient for study of Aim 3, which is designed to show that tDCS+-rehab is at least as safe and feasible (no greater attrition or probability of guessing the group) as rehabilitation given alone (sham+-rehab).

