## **9.4 Data Analysis Plan**

For aim 1, measures of function, strength/muscle power, dexterity, sensation, prehension, perception of independence in self-care, and quality of life will be collected, while for aim 2, metrics characterizing neurophysiology will be acquired and for aim 3, vital measurements will be noted daily.

Functional metrics adopted here are part of the National Institute of Neurological Disorders and Stroke (NINDS) Common Data Elements (CDEs), developed through the collaboration of the International Spinal Cord Society, the AIS, and the NINDS. The functional metrics span across all domains of the World Health Organization's (WHO's) International Classification of Function (ICF) model, including body function and structure, activity limitations, and participation restrictions. Metrics include Graded Redefined Assessment of Strength, Sensibility and Prehension (GRASSP), comprising the Upper Extremity Motor Score (UEMS) for strength, Nine-hole peg test (NHPT) for dexterity and sensation and prehension; Wolf Motor Function Test (WMFT) for measurement of functional abilities; Spinal Cord Independence Measure (SCIM) for evaluation of patient's ability to perform self-care; Canadian Occupational Performance Measure (COPM) to identify the patient's perceived level of daily participation in functional activities (e.g. cooking, cleaning, and hobbies). Each set of tests gives a different perspective of disability and testing all will allow us to get a full picture of patient function and quality of life before and after therapy. All measurements for aim 1 will take 120-150 min to complete. We will determine whether patients receiving tDCS in conjunction with rehabilitation experience greater recovery of function and independence than patients who receive rehabilitation alone (aim 1).

In aim 2, we will study the patient's neurophysiology, which will include the study of excitability of output pathways to a weaker muscle and a stronger muscle, and the cortical representations of these muscles. These measures of neurophysiology will be acquired using TMS and Hoffman or H-reflex. Neurophysiological tests will take 150-180 min to complete, which includes time allotted for breaks. We will test whether patients receiving tDCS in conjunction with rehabilitation experience greater gains in excitability of substrates devoted

Title: Improving Spinal Cord Injury Rehabilitation Interventions by Retraining the Brain

PI: [name]

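### Two pre-tests are collected from each patient, but the plan gives neither a stated role in the efficacy analysis and names no model, baseline value or site term

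*Combined protocol and SAP*

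**What the plan says.** - **Visits (5.1).** "Assessments will be completed before and after the baseline control phase (pretests 1/2), the intervention phase (posttest) and the 3-month follow-up phase (follow-up"). Sections 7.1a and 7.2 describe both pre-tests as full functional and neurophysiology batteries, each over two days.
- **Sizing (5.2).** The pilot effects are used to "estimate sample sizes, based on two sample t statistics compiled at" alpha 0.05, "for 80% power (Table 2"). The Aim 1 metrics are "UEMS (# Weak muscles showing clinically detectable improvement") and the "between-group comparison of % improvement on the NHPT (pegs per second"). The Aim 2 metric is the percent change in map ratio. The totals are 40, 32 and 26, and 40 is raised to 44 for 10% attrition.
- **Analysis (9.4).** For Aim 1: "We will determine whether patients receiving tDCS in conjunction with rehabilitation experience greater recovery of function and independence than patients who receive rehabilitation alone". Aim 2 is worded in the same way. No test, model, covariate or baseline value is named.
- **Pilot reliability (4.2).** "Values of UEMS and TMS metrics showed excellent and moderate-to-excellent reliability during the baseline control phase", with concordance coefficients of 0.964 for UEMS and 0.644 to 0.935 for the TMS metrics.
- **Sites (5.1, 7.3a).** Four sites are planned, with 6, 8, 14 and 21 to 25 patients, each with its own prescribing therapist. Site appears in no analysis statement.

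**The concern.** Hypotheses 1 and 2 concern gains, so every efficacy result depends on what counts as baseline. The plan leaves open whether that is pre-test 1, pre-test 2 or their mean. It also leaves open whether baseline enters through a difference, a percent change or a covariate. With two measurements available, several analyses of the same outcome remain possible after the data are seen.

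The second issue is efficiency. With about 20 evaluable patients per arm, residual variance matters. A change from a single pre-test carries all of that visit's measurement error. Regressing on the mean of two pre-tests averages the error and corrects for chance imbalance between arms. The potential gain is largest for the less reliable TMS metrics.

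**Working it through.** **1. The plan's own figure.** A two-sided two-sample t with effect 0.938, alpha 0.05 and 80% power needs 18.85 per arm, so 19 per arm and 38 in total, against 40 stated. All twelve entries of Table 2 reproduce within 2 patients. At 20 per arm the power is 82.4%. For attrition, 40 × 1.10 = 44, and 40/0.90 = 44.4, which rounds up to 45. The sizing stands.

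**2. Inputs for the gain.** Pre-test variance is set to 1. The correlation r between the two pre-tests is taken as the pilot concordance: 0.964, 0.935 or 0.644. The pre-post covariance is assumed equal to r. Between-patient variation in response adds variance h = k(1−r) to the post-test. The values of k (0, 1, 2 and 4) are assumptions.

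**3. Residual variance.**
- Change from one pre-test: 2(1−r) + h
- Change from the mean of both: 1.5(1−r) + h
- Post-test regressed on the mean of both: 1 − 2r²/(1+r) + h

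**4. Results.**

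| r | k | Change from one | Change from mean | Regression on mean | Variance fall vs one (SE fall) | Variance fall vs mean |
|---|---|---|---|---|---|---|
| 0.964 | 0 | 0.0720 | 0.0540 | 0.05367 | 25.5% (13.7%) | 0.6% |
| 0.935 | 0 | 0.1300 | 0.0975 | 0.09641 | 25.8% (13.9%) | 1.1% |
| 0.644 | 0 | 0.7120 | 0.5340 | 0.4955 | 30.4% (16.6%) | 7.2% |
| 0.964 | 4 | 0.2160 | 0.1980 | 0.1977 | 8.5% (4.3%) | 0.2% |
| 0.644 | 4 | 2.1360 | 1.9580 | 1.9195 | 10.1% (5.2%) | 2.0% |

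At k = 1 the fall against one pre-test is 17% to 20%. At k = 2 it is 13% to 15%.

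**5. Power.** Start from 80% at 20 per arm (effect 0.909, 38 degrees of freedom) and spend 4 degrees of freedom, leaving 34. Against change from one pre-test, power becomes 83% to 92%. Against change from the mean of both, it becomes 79.8% to 82.6%.

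**6. A different assumption.** Keep equal SDs at all visits, hold the pre-pre correlation at 0.964, and let the pre-post correlation rp run from 0.4 to 0.9.
- Regression on the mean, 1 − 2rp²/1.964, against change from one, 2 − 2rp: variance falls by 12% to 30%.
- Of this, the second pre-test itself (regression on two against regression on one, 1 − rp²) contributes only 0.3% to 8%.
- Against change from the mean, 1.982 − 2rp: the fall is 29% at rp = 0.4 (0.837 against 1.182) and 4% at rp = 0.9 (0.175 against 0.182).

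The answer therefore depends on the comparator and on the unreported pre-post correlation.

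**The case against.** A reader might infer that the trial will be analysed by an unadjusted t-test, that one pre-test is discarded, and that 10% to 30% of precision is lost. The documents do not support this, for four reasons.

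- Section 5.2 offers the t statistic as a basis for sample size and never calls it the analysis. Section 9.4 is silent, and silence is not a decision to drop a pre-test. Section 10.1b mentions an interim analysis plan and a statistician, but that plan is not among the documents.
- The sizing metrics are gains or percent changes, so they already contain a pre-treatment value. What is missing is baseline as a covariate.
- The larger figures hold only against change from one pre-test. The text equally permits change from the mean of both. If the pre-post correlation equals the pilot reliability, little is then left to gain.
- The second pre-test has another evident purpose. It closes a baseline control phase, which in the pilot served to show stability without intervention.

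Two further limits stand. Equating the pre-post correlation with the pilot concordance is favourable, because that figure comes from a 14-patient pilot with a 2-week untreated phase, while here a 3-week intervention lies between pre-test and post-test. The formulas also assume continuous measures with equal SDs, so they are only approximate for muscle counts and percent changes. No gain from a site term has been calculated.

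None of this supplies the missing model or baseline definition, and a stability purpose does not prevent averaging the two pre-tests.

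**Conclusion.** The point holds as a gap in specification with an inexpensive improvement available. Two pre-tests are collected, neither has a stated role in the efficacy analysis, and no model, baseline value or site term is named.

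The size must be given as a range that depends on assumptions:
- Against change from one pre-test, residual variance falls by about 8.5% to 30% and the standard error by about 4% to 17%.
- Against change from the mean of both, variance falls by about 0.6% to 7% if the pre-post correlation equals the pilot concordance (0.964 to 0.644). It falls by less if response also varies independently between patients. It could fall by more if the pre-post correlation were well below the pre-pre correlation with unchanged SDs.

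These are variance figures and should not be read as an equal loss of precision on the standard-error scale. A reader might also conclude that 44 patients is the wrong number. It is not wrong on this account, because the sizing calculation reproduces and does not rely on covariate adjustment.

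**What to change.** State in section 9.4 that each continuous Aim 1 and Aim 2 outcome is analysed by a linear model of the post-test value on arm, the mean of pre-tests 1 and 2, and site. Where post-test and 3-month values both exist, use a mixed model with the same covariates. For neurophysiology this will cover only some patients, because section 7.1a makes the 3-month measurement optional. State also how a patient with only one pre-test is handled. Keep the two-sample calculation in section 5.2 as the conservative sizing basis.

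The cost is plan wording, settled before unblinding. No visit or measurement is added. The model spends about 4 degrees of freedom (one for baseline, three for four sites) out of 38 to 42 with 40 to 44 evaluable patients. At 20 per arm that lowers power from 80.0% to 79.8% if the covariates explain nothing.

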## 4. REPORT OF PRIOR INVESTIGATIONS

### 4.1 Summary of Previous Studies

Our recent published and preliminary work funded by the DoD and the Conquer Paralysis Now foundation indicates that tDCS can be effective for enhancing rehabilitative outcomes in SCI [59-62]. In a pilot, randomized, double-blinded, placebo-controlled clinical trial, we allocated 14 patients with C2-C6 incomplete SCI ( $\geq 1$  year post injury; having sparing to muscles in the upper extremities below the level of injury) to either receive tDCS (n= 8) or sham tDCS (n= 6) during rehabilitation. Interventions were given for 2 hours/day, 5 days/week for 2 weeks. Before receiving these interventions, patients completed a baseline control phase lasting 2 weeks, during which they continued with the typical routine. After receiving the interventions, patients completed a 3-month follow-up phase, during which they engaged in a home exercises prescribed by the physical therapist (PI, [name]).

Outcomes included metrics specified in the Common Data Elements (CDEs), developed through the collaboration of the International Spinal Cord Society, the AIS, and the National Institute of Neurological Disorders and Stroke (NINDS). The primary outcome was the Upper Extremity Motor Score (UEMS), which rates power/strength of 10 muscles of the arm and hand, each on a 0-5 scale of the UK's Medical Research Council (MRC; 0, no voluntary twitch; 5, maximum contraction against resistance). The sum total ranges between 0 and 50. The secondary outcome was fine-motor control or dexterity tested using the Nine-Hole Peg Test (NHPT), which requires patients to place tiny pegs into holes on a board, then remove and replace them as quickly as possible. Neurophysiologic metrics were also collected, with the use of TMS. Excitability of motor cortical maps and residual corticospinal pathways was quantitated for strong muscles above the level of injury (C3-C6) and weak muscles below that level (C6-T1).

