#### 6.1a General Inclusion Criteria

Patients with incomplete (having sparing to muscles in the upper extremities below the level of injury) C1-C8 SCI; age  $\geq 18$  years;  $\geq 1$  year time post injury (to avoid confounding effect of cervical root recovery [77]) will be enrolled. On the more affected side, patients will be required to have sparing of either the biceps or the triceps muscle, defined as  $\geq 3$ -muscle power grade on the MRC scale. They will also be required to show weakness of the muscle antagonist to the spared muscle i.e. triceps in case of spared biceps, or biceps in case of spared triceps on the affected side. Weakness will be defined as a MRC grade of 1-3, and a clinically detectable difference in power compared to the power of the spared muscle, i.e.,  $\geq 1$  muscle grade lower on the MRC scale [63, 64]. Criteria requiring sparing of one muscle and the weakness of the antagonist muscle are meant to create a homogeneous sample for the study of neurophysiology using TMS in Aim 2. These criteria will not be limiting for subject recruitment, as evident from the successful completion of our recent pilot work, because patients with cervical SCI either commonly show sparing of biceps (C5) and weakness of triceps muscles (C7), or this order of weakness is reversed in patients with central cord syndrome [60, 61]. On the contrary, these criteria will allow inclusion of even more-impaired individuals, who may not have “active hand function” as required by typical SCI studies [66, 68] and an ongoing study (NCT02611375).

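### The muscle count behind N = 40 has a different ceiling for each patient: the 80% power assumes the pilot's case mix, and an unadjusted comparison of the count is inefficient

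*Combined protocol and SAP*

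**What the plan says.** Section 5.2 uses the pilot effect sizes to "estimate sample sizes, based on two sample t statistics compiled at" a 5% level. The first row of Table 2, "UEMS (# Weak muscles showing clinically detectable improvement"), carries an effect size of 0.938. The text under the table describes that row's metric: "Based on between-group comparison of the numbers of weak (C6-T1) muscles that achieved clinically detectable improvements on MRC". On that row, "we would require a total of 40 patients", the largest 80% requirement of the three metrics. Then: "Considering that there could be attrition of 10%, we expect to enroll 44 patients". No denominator, proportion or adjustment for the number of muscles weak at baseline is mentioned.

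Section 6.1a requires one spared muscle (MRC 3 or more) and a weak antagonist, "i.e. triceps in case of spared biceps, or biceps in case of spared triceps on the affected side". It sets no minimum number of weak C6-T1 muscles. Sections 5.4 and 6.1a label the biceps C5, and 6.1a expects the weak-biceps pattern in central cord syndrome.

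The pilot, in section 4.1: "we allocated 14 patients with C2-C6 incomplete SCI". The present trial, in section 5.1: "C1-C8 SCI will be enrolled across 4 sites".

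Section 5.2 names GRASSP as the primary outcome for Aim 1 and uses the count because strength is one of its components. Section 9.4 lists the measures and the group comparisons but gives no statistical model or covariate.

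**The concern.** A count of improved weak muscles mixes two things: how many muscles could improve, which is fixed before treatment, and how many did. The first is noise for a treatment comparison. The entry criteria let it vary widely. A patient who qualifies on a weak biceps can recover exactly that muscle and gain nothing on the count, and with no weak C6-T1 muscle would score zero in either arm.

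Two things are at stake. Power is given away if the count is compared without regard to its ceiling. And 0.938 transfers to this trial only if the spread of ceilings, including any zeros, resembles the pilot's.

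**Working it through.** **Step 1. The plan's own figure.** Inputs from Table 2: d = 0.938, alpha 0.05, power 80%, equal arms. A two-sided two-sample t test (noncentral t) needs 19 per arm, 38 in total, against the stated 40. The other Table 2 cells also come out within two patients. Power at d = 0.938 is 82% with 20 per arm, 86% with 22, 89% with 24 and 92% with 27. The stated size follows from the stated effect.

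**Step 2. What case mix could do.** The documents give no ceilings, count means or share of patients with nothing to count, so this step is an assumption. Let a share *f* of both arms, beyond whatever share the pilot had, be fixed at zero. In the remaining patients let the SD be 1, the sham mean *m* and the active mean *m* + 0.938. Then:

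- difference = (1 − f) × 0.938
- variance in an arm = (1 − f) + f(1 − f) × (arm mean)²
- diluted d = difference / √(average of the two variances)

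Example, f = 0.10 and m = 1: difference 0.844; active variance 0.9 + 0.09 × 1.938² = 1.238; sham variance 0.9 + 0.09 × 1² = 0.990; SD √1.114 = 1.055; d = 0.80.

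| Extra zeros | d (m = 1 to 0.5) | Power, 20 per arm | N for 80% |
|---|---|---|---|
| 0% | 0.938 | 82% | 38 |
| 5% | 0.86-0.89 | 76-78% | 46-42 |
| 10% | 0.80-0.84 | 69-74% | 52-48 |
| 20% | 0.69-0.76 | 57-64% | 68-58 |

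With m = 1.5 and f = 10%, d is 0.75 and power 64%. If the trial's mix matches the pilot's, the first row applies and nothing is lost.

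**Step 3. What adjustment gains.** This does not depend on the pilot's mix. Assumptions: 20 per arm; number of weak muscles uniform over the range shown; chance of a one-grade gain per muscle 25% on sham and 55% on active; muscles independent or with within-patient correlation 0.4 (beta-binomial). The raw t test is compared with a linear model that adds the baseline number of weak muscles as covariate.

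| Weak muscles | Independent: raw → adjusted | Correlation 0.4: raw → adjusted |
|---|---|---|
| 2-4 | 88% → 91% | 66% → 68% |
| 1-4 | 75% → 85% | 56% → 61-62% |
| 0-4 | 54% → 75% | 41% → 52% |

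At 25% against 50% with 1-4 muscles, the gain is from about 61% to 71% (independent) and 43% to 48% (correlation 0.4). Over all these settings it runs from about 1 point, when ceilings hardly vary, to about 21 points, when zeros are common. Type I error is about 5% for both methods. Only the difference between methods is informative here; the absolute levels follow from the assumed rates and do not test the plan's 80%.

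**Step 4. A proportion instead.** Pooling muscles in a plain binomial comparison (1-4 muscles, null rate 35%, 20 per arm) gives type I error of about 5% with independent muscles, 10% at within-patient correlation 0.2 and 15% at 0.4. It ignores that muscles of one patient move together.

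**The case against.** The tempting stronger reading is that the trial has less than its stated 80% power. The documents do not support it. The 0.938 is a standardised effect on this same count, so its SD already contains the pilot's variation in ceilings. Section 6.1a cites the pilot for the reversed pattern, so weak-biceps patients may already be in it. Widening to C1-C8 has no stated net effect. On level alone, C7-C8 injuries leave fewer C6-T1 segments below the lesion and C1 injuries do not, but the expected mix of levels and severities is not given. The losses in step 2 are therefore conditional. All of this stands.

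A reader might also infer that weak-biceps patients must score zero. They need not: a spared triceps may be only grade 3, other C6-T1 muscles may be weak, and section 5.2 does not limit the count to one limb. It is also possible that the word weak in section 5.2 names the C6-T1 group as a whole and not a list per patient. Ceilings would still differ, because a muscle already at grade 5 cannot gain a grade, but zeros would be rarer.

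Nor does chance imbalance in the number of weak muscles produce a spurious treatment effect: randomisation holds type I error at 5%.

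Two further limits stand. The count is not a named endpoint, so the inefficiency arises only if it is analysed. And section 5.1 now enrols 49 to 54 patients. If all are randomised, 54 less 10% leaves about 24 per arm, which gives 81% at d = 0.84 and 77% at d = 0.80. That cushion is partial, and the same section still gives 22 per arm.

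**Conclusion.** The point holds in a limited form. The metric that fixes N = 40 is a raw count whose maximum varies by patient and can be zero, and for a patient entering on a weak biceps the qualifying muscle is never counted. The stated N is arithmetically sound, and no shortfall below 80% is shown. What the documents leave open is whether the C1-C8 mix has the pilot's ceilings. What can be improved in any case is the comparison: adjusting for the baseline number of weak muscles is worth roughly 1 to 21 points of power in the settings tried (about 10 points with 1-4 independent muscles, 5 to 6 at correlation 0.4), with type I error unchanged. Those sizes rest on assumed rates, ceilings and correlations, none of which the documents supply.

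**What to change.** In sections 5.2 and 9.4, wherever the count is analysed:

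- Define a weak muscle for this purpose, and fix each patient's set from grades taken before randomisation.
- Compare arms with a linear model that adjusts for the baseline number of weak muscles. If a proportion is modelled instead, use a method that allows for within-patient correlation, not a plain binomial model.
- Report the baseline number of weak C6-T1 muscles by arm, including how many patients have none.
- State that 80% power at 40 patients assumes the pilot's C2-C6 mix.
- If the qualifying biceps is added to the set, or the count is limited to one limb, say that 0.938 no longer applies directly, since it belongs to a different metric.

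The cost is wording. UEMS and MRC grades are already recorded at screening, and GRASSP, which includes strength, at the pre-tests, so no new data or visits are needed. The power statement becomes conditional and reads slightly less favourably. Changing the muscle set costs more, because the new metric has no pilot effect size in the protocol.
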